## 9. STATISTICAL ASPECTS

### 9.1. SAMPLE SIZE CALCULATION

Primary endpoint is the reduction on migraine crisis frequency before and after music therapy.

In the population of patients corresponding to inclusion criteria, mean number of migraine crisis per month can be estimated to 8 (standard deviation = 4) before intervention.

A reduction clinically significant would be a reduction of at least 50% of mean monthly number of migraine crisis after 3 months of care.

Under these conditions, 20 patients are needed to have this difference of 50% with a statistical power of 90% and an alpha equal to 5%.

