## 4. STUDY DESIGN

### 4.1. METHODS

Monocentric, prospective before-after study.

It comprises of only one group of patients and all of them will receive the intervention.

The study will measure and compare migraine frequency during the month before inclusion with migraine frequency 3 months after the inclusion.

- **Entry in the study:** based on proposition of algologist doctor involved in the patient care and after patient receives information and signs inform consent.

- **Inclusion period:** the month before the initiation of music session will serve as reference period. Patient will fill migraine diary, complete questionnaires on functional and emotional impact used usually in the department.

The following endpoints will be evaluated:

- migraine severity (number of days with migraine, duration, intensity, treatment)
- questionnaire HAD to evaluate emotional impact
- questionnaire HIT to evaluate functional impact

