### 7.1. PRIMARY ENDPOINT

**Reduction of migraine crisis frequency of at least 50% after 3 months of treatment.**

The studied variable will be the monthly frequency of migraine crisis. Data collection will be done using a migraine agenda (annex 1), starting the month before inclusion and music therapy initiation. This agenda

should then be completed usually during study period under music therapy. During each monthly visit, a control will be done by the intern of general medicine associated to the study.

The primary endpoint will be obtained using the difference between mean crisis frequency during the month before music therapy initiation and the one obtained during the 3rd month of treatment.

A reduction of at least 50% at month 3 will be considered as music therapy efficacy on episodic migraine prevention.

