#### Analysis of primary endpoint

Monthly mean number of migraine crisis before music therapy will be compared to the one obtained at Month 3 using Wilcoxon signed rank test for paired (dependent samples). The analysis will be performed in intent-to-treat.

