3.1. PRIMARY ENDPOINT

Reduction of migraine crisis frequency of at least 50% after 3 months of treatment.

The studied variable is the monthly frequency of migraine crisis. Data collection is done using a migraine agenda (annex 1 of protocol), starting the month before inclusion and music therapy initiation. This agenda should then be completed usually during study period under music therapy. During each monthly visit, a control will be done by the intern of general medicine associated to the study.

The primary endpoint is obtained using the difference between mean crisis frequency during the month before music therapy initiation and the one obtained during the 3rd month of treatment. A reduction of at least 50% at month 3 is considered as music therapy efficacy on episodic migraine prevention.

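### The stated 90% power belongs to the test of no change, not to the 50% efficacy criterion, which a true 50% fall meets only about half the time at any sample size

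*Protocol*

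**What the plan says.** The design has a single arm (protocol 4.1): "It comprises of only one group of patients and all of them will receive the intervention". Three statements bear on this point.

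- **Sample size (protocol 9.1; same text in SAP 5.1).** At baseline, "mean number of migraine crisis per month can be estimated to 8 (standard deviation = 4) before intervention". The clinically significant effect is "a reduction of at least 50% of mean monthly number of migraine crisis after 3 months of care". From these, "20 patients are needed to have this difference of 50% with a statistical power of 90% and an alpha equal to 5"%.
- **Efficacy criterion (protocol 7.1).** "The primary endpoint will be obtained using the difference between mean crisis frequency during the month before music therapy initiation" and the corresponding figure for the third month of treatment. Then: "A reduction of at least 50% at month 3 will be considered as music therapy efficacy on episodic migraine prevention". SAP 3.1 agrees: "A reduction of at least 50% at month 3 is considered as music therapy efficacy on episodic migraine prevention".
- **Analysis (protocol 9.2; same in SAP 5.2).** The monthly mean before music therapy is "compared to the one obtained at Month 3 using Wilcoxon signed rank test for paired (dependent samples"). The test contains no 50% threshold.

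Neither document says which null hypothesis the 90% refers to. Neither plans a confidence bound or test against 50%, and neither says how the test and the 50% criterion are to be combined.

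**The concern.** The same 50% does two jobs. In the sample size section it is the assumed true effect. In the endpoint section it is the level that the result must reach to count as efficacy. Protocol 9.1 attaches the 90% to obtaining a 50% difference, so a reader who sets it beside 7.1 will conclude that a treatment which truly halves crises would meet the criterion nine times in ten.

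That conclusion would be false. When the assumed effect sits exactly on the threshold, the estimate falls on either side of it about equally often. The misreading matters because there is no control group, so the 50% criterion carries much of the weight of any efficacy claim.

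**Working it through.** **Inputs from the documents.** Baseline mean 8 and SD 4; planned fall 50%, that is 8 to 4, a difference of 4; n = 20; power 90%; alpha 5% with sidedness not stated (protocol 9.1, SAP 5.1).

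**Inputs not in the documents.** The Month 3 SD, the within-patient correlation ρ and the SD of the change. They are treated below as assumptions and varied.

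**Step 1: reproduce the plan's figure as a test of no change.** With SD 4 at both times, the SD of the change is 4·√(2(1−ρ)). At ρ = 0 this is 5.66. The normal approximation is n = (z_α + z_β)²·SD²/4².

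- Two-sided: (1.960 + 1.282)² × 32/16 = 21.02, rounded up to 22.
- One-sided: (1.645 + 1.282)² × 32/16 = 17.1, rounded up to 18.
- Power at n = 20, two-sided: Φ(4·√20/5.66 − 1.96) = 88.5%.

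The stated 20 patients and 90% are therefore close to what a test of no change gives at ρ = 0. Other assumed correlations at n = 20, two-sided, give:

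| ρ | SD of change | Paired t power | Simulated Wilcoxon power |
|---|---|---|---|
| 0 | 5.66 | 85% | 84% |
| 0.25 | 4.90 | 93% | 92% |
| 0.5 | 4.00 | 99% | 99% |

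**Step 2: probability of meeting the 50% criterion.** Let r be the true proportional fall. The observed mean fall is at least 50% when the mean of (post − 0.5·pre) is at or below zero. Its expectation is 8(1−r) − 4 = −8(r − 0.5). Its variance per patient is V = S² + 0.25·4² − ρ·4·S, where S is the Month 3 SD. So

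P = Φ( 8(r − 0.5) / √(V/n) ).

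At r = 0.5 the numerator is zero and P = Φ(0) = 50%. V and n drop out, so no choice of SD, correlation or sample size changes it. Simulations at n = 10, 20, 50 and 200 gave 49% to 51% with normal data and 49% to 54% with negative binomial counts. The small excess over half comes from skewness and from ties counted as meeting the criterion. Requiring a significant Wilcoxon result as well gave 49% to 51% at n = 20.

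**Step 3: true fall needed for a 90% chance of meeting the criterion at n = 20.** Solve 8(r − 0.5) = 1.2816·√(V/20). For example, with S = 4 and ρ = 0, V = 16 + 4 = 20, so √(V/20) = 1 and r = 0.5 + 1.2816/8 = 0.660.

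| ρ | S fixed at 4 | S = 4(1−r) |
|---|---|---|
| 0 | 66.0% | 59.2% |
| 0.3 | 64.0% | 57.9% |
| 0.5 | 62.4% | 56.7% |
| 0.7 | 60.6% | 55.3% |

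The range is roughly 55% to 66%, and it depends wholly on the assumed Month 3 SD and correlation.

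**Step 4: can the test and the criterion disagree?** By the t approximation at n = 20, the smallest significant mean fall is 2.093·SD/√20. With SD of change 5.66 this is 2.65 crises, or 33% of 8. With SD 4.00 it is 1.87 crises, or 23%. An observed fall between those values and 50% would be significant and still below the criterion.

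**The case against.** The strongest reply is that there is no arithmetic error. Power paired with an alpha is the language of a hypothesis test, and the only primary test is the paired Wilcoxon. Read that way, 9.1 means 90% power to reject no change if the true fall is 50%, and Step 1 shows that to be about right. Setting the planning effect at the smallest clinically relevant change is also ordinary practice. This stands: 20 patients is not shown to be wrong, and a reader who infers a miscalculated sample size goes beyond the documents. What remains is that 9.1 names no null hypothesis and words the power as that of obtaining the 50% difference which 7.1 makes the mark of efficacy.

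A second reply is that the 50% may be a per-patient responder rule. The recommendation cited in protocol section 7 could be read so, and the cohort study in protocol section 2 is reported as a share of patients with at least a 50% decrease. But 7.1 and 9.1 both speak of means, so the group reading has the better textual support. On the per-patient reading, about 50% to 63% of patients would be responders in the simulations under the planned effect. No required responder proportion is stated, so the 90% has nothing to attach to.

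Third, a reader might infer that a true halving which happens to show as 45% would be reported as lack of efficacy. The documents do not say so. They say what a fall of at least 50% will be taken to mean, and are silent on a smaller fall that is statistically significant.

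**Conclusion.** The point holds as a misattributed power statement. The 90% is approximately the power of the paired test against no change at a true 50% fall: about 85% to 99% at n = 20, given SD 4 at both times and a correlation of 0 to 0.5, neither of which the documents supply for Month 3. It is not the probability of meeting the criterion in protocol 7.1 and SAP 3.1. On the group-mean reading that probability is about 50% at a true 50% fall, and this result needs no assumption about SD, correlation or sample size beyond a roughly symmetric sampling distribution. Enlarging the trial would not raise it. The role of the criterion relative to the test is also left open, and the two can disagree.

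**What to change.** In protocol 9.1 and SAP 5.1:

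1. State that the 90% refers to rejecting no change with the paired test when the true mean fall is 50%.
2. Add that, under the same true fall, the chance of an observed mean fall of at least 50% is about 50%.
3. If a further operating figure is wanted, label it as assumption-dependent: at n = 20 a 90% chance of observing at least 50% would need a true fall of roughly 55% to 66%, for a Month 3 SD either scaled with the mean or fixed at 4 and a correlation of 0 to 0.7.

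In protocol 7.1 and 9.2 and SAP 3.1 and 5.2, state which of the two, the test or the 50% criterion, supports the efficacy conclusion, and what is concluded when they disagree. If the 50% is meant per patient, say so and give the required responder proportion.

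The cost is a few sentences in each document and a less favourable description of the criterion. On the group-mean reading, patient number, data collection and the planned test stay as they are.

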### 9.2. STATISTICAL METHODS

#### Baseline characteristics

Baseline characteristics will be summarized. Qualitative variables will be described using number of patients, percentage and 95% confidence interval (IC95%). Quantitative variables will be described as number of patients, mean, standard deviation, confidence interval of the mean, median, Q1, Q3, minimum and maximum.

#### Analysis of primary endpoint

Monthly mean number of migraine crisis before music therapy will be compared to the one obtained at Month 3 using Wilcoxon signed rank test for paired (dependent samples). The analysis will be performed in intent-to-treat.

#### Analysis of secondary endpoints

Quantitative variables measured before music therapy will be compared with the ones collected after music therapy using the same statistical method as for primary endpoint.

Qualitative variables (proportions) measured before music therapy will be compared with the ones collected after music therapy using McNemar Chi test.

All the tests will be realized with SAS 9.2 software with  $\alpha = 5\%$ . A statistical analysis plan will be prepared and will detailed the different analyses.

---

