#### - **Final evaluation at Month 3**

Diary data of the third month will serve for this evaluation according to the guidelines of the International Headache Society:

- number of days with migraine (primary endpoint)
- duration and intensity of migraine
- medication consumption
- emotional impact: score HAD
- functional impact: score HIT.

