## 7.2. SECONDARY ENDPOINTS

### - Reduction of crisis intensity and duration, as well as medication consumption.

Crisis intensity (mild, moderate, severe), duration in hour, and the number of treatments taken will be collected in the migraine agenda (annex 1) filled by the patient. These variables will be compared between the month before music therapy initiation and the 3rd month of treatment.

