### - Reduction of functional and emotional impact.

Questionnaires HAD and HIT (annex 2) will be completed with the investigator during the inclusion visit before initiation of music therapy, and at Month 3 visit.

- Questionnaire HAD to evaluate emotional impact (national reference HAS « chronic pain: recognize chronic pain syndrome, evaluate it and guide the patient »)
- Questionnaire HIT to evaluate functional impact (guideline of the International Headache society)

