#### MIGRAINE DIARY

Please fill in the migraine calendar daily and specify each day:

Migraine

Headache intensity: mild, moderate or severe

Duration in hours of headache

Migraine treatments used

Date	Migraine/tension headache	Intensity	Duration	Treatments
D1				
D2				
D3				
D4				
D5				
D6				
D7				
D8				
D9				
D10				
D11				
D12				
D13				
D14				
D15				
D16				
D17				
D18				
D19				
D20				
D21				
D22				
D23				
D24				
D25				
D26				
D27				
D28				
D29				
D30				
D31				

## 16.2. APPENDIX 2

Please fill the 2 questionnaires below:

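### Must the plan define how daily diary intensity and duration become one value per patient, and which variable the McNemar test is for?

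*Protocol*

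**What the plan says.** Protocol 7.2 lists intensity, duration and number of treatments as diary outcomes and adds: "These variables will be compared between the month before music therapy initiation and the 3rd month of treatment". SAP 3.2 says the same. A second group of outcomes, headed "Reduction of functional and emotional impact", uses the HAD and HIT questionnaires.

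The diary (Protocol Appendix 1) has one row per day, D1 to D31. Its instruction is "Please fill in the migraine calendar daily and specify each day", and one of the items is "Duration in hours of headache".

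Protocol 9.2 sends quantitative secondary variables to the same paired Wilcoxon test as the primary endpoint. For the rest it says: "Qualitative variables (proportions) measured before music therapy will be compared with the ones collected after music therapy using McNemar". It then promises: "A statistical analysis plan will be prepared and will detailed the different analyses". SAP 5.2 repeats the two test sentences and adds nothing to them.

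**The concern.** A paired test needs one number per patient per period. Eligibility requires at least 4 attacks a month, so every patient brings several baseline values of intensity and duration, and no rule reduces them to one. The SAP was meant to supply the detail and does not.

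The McNemar test needs a paired yes/no variable, and none is named. The only yes/no quantity in the plan, a fall in frequency of at least 50%, has no before value.

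The stake is interpretation. Some summaries grow with the number of crises. If frequency falls, as the trial hopes, such a summary falls too. The result could then be reported as shorter or milder crises when only their number has changed. A choice made after seeing the data could lean that way.

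**Working it through.** There is no stated figure to reproduce. The check has four parts.

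**1. Does the choice of summary matter at all?** Take one invented patient, with crisis durations in hours:
- Baseline: 4, 4, 6, 24, 4, 8, 4, 6. Total 60, mean 60/8 = 7.5, median 5, longest 24.
- Month 3: 6, 24, 8, 6. Total 44, mean 44/4 = 11.0, median 7, longest 24.

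Mean and median worsen, the total improves and the longest is unchanged. So the choice can matter.

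**2. How many plausible summaries mislead?** Simulation with 20 patients per trial:
- Baseline crises: Normal with mean 8 and SD 4 (Protocol 9.1), rounded and restricted to 4-14 (eligibility).
- Month 3 crises: binomial, each baseline crisis kept with probability 0.5.
- Intensity (assumed): three grades from a latent normal, 25% mild and 20, 30 or 40% severe.
- Duration (assumed): lognormal, median 12 h, within-patient log SD 0.4 to 0.8.
- No true change in intensity or duration. 12 settings, 2,000 trials each, nominal error 5%.

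| Variable and test | Summary | Rejected |
|---|---|---|
| Duration, signed-rank | mean hours | 4-6% |
| | median hours | 5-7% |
| | longest crisis | 21-43% |
| | total hours | 96-100% |
| Intensity, signed-rank | mean score | 4-6% |
| | median score | 4-7% |
| | share severe | 4-6% |
| | worst grade | 15-32% |
| Intensity, McNemar chi-square | more than half severe | 2-5% |
| | at least half severe | 4-10% |
| | median at least moderate | 4-10% |
| | any severe crisis | 17-31% |

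Eight of the 12 stay at or below 10%. The other four depend on the number of crises. With no fall in frequency, total hours rejected in 4-6% and any severe crisis in 2-6%, so the excess comes from frequency.

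**3. Which reading does the text support?** Protocol 7.2 describes the intensity of a crisis and its duration in hours. The data list in Protocol 11.1 marks headache days and medication as monthly quantities, but lists duration and intensity as attributes of crises, with no monthly qualifier. This points to a typical value per crisis, not a monthly total. A mean or median is the ordinary way to obtain it, and those rows of the table sit near 5%.

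For the McNemar sentence, take the six secondary variables in turn: intensity has three ordered grades; duration is in hours; treatments are a count; HAD gives two totals; HIT-6 is a score from 36 to 78. None is yes/no, so 0 of 6 call for McNemar. The five numeric ones fall under the Wilcoxon sentence, and intensity does too once its grades are scored. The McNemar sentence is a standing rule for a type of variable that the plan does not contain.

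**4. Would a more detailed rule be safer?** Not necessarily. The diary has no crisis number and no start or stop time. A 36-hour crisis starting at 18:00 fills three rows (6 + 24 + 6 = 36 h), or 36/3 = 12 h per day. The natural rule for rebuilding crises is to join consecutive migraine days and sum their hours. But separate attacks on neighbouring days are joined more often when attacks are frequent. With one-day crises placed at random over 30 days (assumed) and 400 trials per setting, mean hours under that rule rejected in 43-47% of trials when crises halve and 17-23% at a 25% fall. Mean hours per migraine day rejected in 4-5% and 6-8%. A rule that looks precise can therefore do worse than a plain average.

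**The case for a change.** The case for a change is respectable. The trial has one arm, everyone knows the treatment, and the principal investigator codes and freezes the data before they go to the statisticians (Protocol 11.4). Specification in advance is the main safeguard left. The protocol promised detail that the SAP does not give, and a few lines would supply it at no cost in data. The wording that suggests a per-crisis quantity does not name the statistic.

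All of that stands as description. It does not show that the planned analysis will mislead. Harm needs an analyst to pick one of four summaries that the plan never mentions and then to describe it wrongly, for example by reporting total monthly hours as shorter crises. A report that names its summary lets the reader see this.

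Patients with no migraine in Month 3 are a smaller loose end. About 0.2 of 20 are expected if crises halve, and 2.3 of 20 if they fall by 75%. In the latter case, scoring them as zero raises rejection to 10-14% for intensity and 12-19% for duration, against 4-6% and 4-8% when they are left out. A patient without migraine has no crisis to grade or time, so leaving them out and counting them is the natural handling.

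One neighbouring matter is not settled here. Protocol 4.1 gives "number of days with migraine (primary endpoint" as the Month 3 measure, while Protocol 7.1 says "The studied variable will be the monthly frequency of migraine crisis". That difference, and the diary column that mixes migraine with tension headache, bear on the primary endpoint and should be judged there.

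**Conclusion.** The omission is genuine, but no change to the plan follows. It concerns two secondary endpoints and is a gap that an analyst fills sensibly: a mean or median per patient and period, tested with the signed-rank test already planned. The sentence on McNemar is left without a variable and does no harm. Sound summaries outnumber misleading ones by 8 to 4 in the set examined. The misleading ones are not in the plan, and the text points away from the worst of them, total hours.

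The rejection rates rest on assumed intensity and duration distributions and on independent loss of crises. The figures for joining consecutive days rest on random placement of one-day attacks and would differ if attacks cluster. A per-crisis average could also shift if music therapy prevented mainly mild crises; this was not simulated, and it is a reason to read these outcomes beside the primary result. Readers of the results should look at which summary was used.

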## **10. SOURCE DATA AND DOCUMENTS ACCESS RIGHTS**

### **10.1. DATA ACCESS**

The administrator is in charge to obtain the agreement of all the parties implicated in the research in order to guarantee direct access to source data, reports and documents everywhere the study is conducted in case of quality control and audit.

Corresponding people will provide documents and individual data if requested to the person authorized to access them to follow laws and regulations in place.

### **10.2. SOURCE DATA**

Source data or document is defined as any original document which allow to demonstrate the existence, or the accuracy of a data collected during the research.

Source documents come from:

- Case Report Form
- Questionnaires filled during inclusion visit: diagnosis, HAD and HIT impact
- Migraine diary, filled the month before inclusion and during 3 months under intervention
- End of study questionnaires: HAD and HIT

### **10.3. DATA CONFIDENTIALITY**

In accordance with the law in force, persons with direct access to the source data shall take all necessary precautions to ensure the confidentiality of the information relating to the search, the persons to whom they belong, as regards their identity and the results obtained. These individuals, along with those who direct and oversee the research, are subject to solicitor-client privilege.

During or at the conclusion of the research, data collected on those who are suitable for it and transmitted to the administrator by those who direct and supervise the research (or any other specialized stakeholders) will be codified. Under no circumstances should the names of the persons concerned, or their addresses be clearly indicated.

Procedures for coding patients:

- only the first letters of the patient's name and first name will be recorded, accompanied by a number indicating the order of inclusion of patients from 01 for the first patient to 20 for the twentieth patient.

The administrator will ensure that each person who is suitable for research has been informed about access to the individual data about them and strictly necessary for the quality control of the research.

